## Document History

Document	Version Date	Summary of changes and rationale
Version 3	07MAY2018	
Administrative changes and the removal of EKG tests.
 
Protocol Updates:
 
 
• Updated version date in footer.
 
• Page 1, Protocol version date: changed to v3, date 07MAY18
 
• Page 7, study synopsis: updated protocol number and NCT number
 
• Page 21, birth control: changed men must not donate sperm to seven months to be consistent with consent
 
• Page 28, 6.1 Table of events: removed 12 lead EKG
 
 
ICF Updates:
 
 
• Updated version date in footer.
 
• Page 3, "End of study": removed EKG
 
• Page 17: added [name]
 

Version 4	11JUL18	
Protocol Updates:
 
 
• Page 2: Added IND number
 
• Page 7, 16, 41: Made the distinction between secondary objectives and exploratory objectives. Note - no new objectives were added.
 
• Page 18 to 19: added additional information to clarify inclusion criteria after feedback received during the SIV: 
 
-Added RCB II or III
 
-Added need to have tissue in the lead institution by C1D1
 
-Added timeline for surgery and radiation completeness
 
-Added info on radiation received
 
-Limited PS to 0-1
 
-Added need for normal thyroid function
 
 
 

		
 
• Page 19 to 20: added additional information to clarify exclusion criteria after feedback received during the SIV: 
 
-Added clarification on autoimmune diseases
 
-Added clarification on definition of active hepatitis B and C
 
 
 
• Page 20: included endocrine therapy to anti-cancer therapies excluded during study
 
• Page 26: added clarification on the dose of nivolumab (was already in the schema but was added to the text)
 
• Page 28: added clarification on the dose of capecitabine (was already in the schema but was added to the text). Added a table with dose modifications for capecitabine
 
• Page 30: table of events - added that pregnancy test is only required for women of child bearing potential only and clarification on type of hepatitis and thyroid function tests required
 
 
ICF Updates:
 
 
• Added the option of research blood work (2 tubes, 10ml each) on C1D2 or C1D3 of study.
 

Version 5	16JAN19	
Protocol Updates:
 
 
• Page 18: added clarification in terms of timing for one of the items of inclusion criteria to be consistent with other inclusion criteria.
 
• Page 27: added new information on preparation of nivolumab based on new IB
 
• Page 29: Table of events. Made changes for consistency with the text. Added clarification on time window for some labs and visits. Added clarification for correlative blood samples (at baseline and not screening) to be consistent with the text.
 

		
 
Page 31: added that surveillance can be done by phone or review of medical records to be consistent with table of events
 
Page 32: removed sentence that was left from the protocol template
 
Page 33: changed from 30 to 100 days for participation of SAEs after discontinuation of dosing per BMS updated protocol guidelines.
 
 
ICF Updates:
 
 
Changes made to include Hackensack as a site
 

Version 6	16JUL2019	
Protocol Updates:
 
 
Page 18, 20, Appendix E: Added Quality of Life Questionnaires
 
Fixed minor administrative discrepancies throughout the protocol
 
Page 34: Made clarifications regarding dose delays for correlative specimen collection
 
Page 35: Clarifications on temporary suspension of treatment and dose interruptions
 
Page 38: Updated the SAE reporting guidelines from BMS for subsites
 
Page 48: Updated specimen labeling section to be consistent with the lab manual
 
 
ICF Updates:
 
 
Page 3-4: Added information on biopsy(ies)
 

Version 6.1	09Mar2020	
Protocol Updates:
 
 
PI changed from [name] to [name] throughout protocol.
 
Section 6.7 removed typo “atezolizumab or placebo”
 
Other Administrative clarifications/corrections made throughout protocol to replace CRO with Multicenter Project Managers and SAE reporting
 
Updates made to incorporate information from Protocol Clarification letters:
 

		
 
• Inclusion Criteria 2 changed “must have” to “should be” and a Note Added for clarification “(Note: As long as tissue sample is confirmed shipped, the subject will be eligible)”
 
• Inclusion Criteria 5 typo correction made
 
• Inclusion Criteria 8 added clarification “(Patients that meet the definition of asymptomatic subclinical hypothyroidism will be eligible to participate)”
 
• Section 6.3 added clarification “Note: Assessments performed for clinical indications (not exclusively to determine study eligibility) may be used for screening/baseline values even if the studies were done before informed consent was obtained.
 

Version 6.2	06 OCT 2020	
 
• Section 1.6.2 Administration of PRO questionnaires corrected to be consistent with table of events
 
• Section 5.2.1: corrected delay of treatment to >42 days to fix discrepancy between this section and Section 6.7. added the term “diarrhea” to be consistent with Appendix D clarified Permanently discontinue nivolumab “unless approved by the Sponsor/Medical Monitor”
 
• Appendix D: GI Adverse Events: updated to be consistent with section 5.2.1 and fixed typographical errors.
 

Version 7	20 Jan 2023	
 
• Section 2.2 (Page 21) Change in the timeframe of one of the secondary endpoints. Given that this study is enriched for a high risk population considered to be relatively refractory to chemotherapy, a 2-year endpoint is considered appropriate. A recently published study that enrolled a similar patient
 

		
population elected 2-year time frame for their clinical endpoints (Schneider BP et al. JCO 2022).
 
CURRENTLY STATES: To determine association between changes in PIS from baseline to week 6 and week 12 and clinical outcome variables (DRFS and OS at 3-years).
 
UPDATED TO: To determine association between changes in PIS from baseline to week 6 and week 12 and clinical outcome variables (DRFS and OS at 2-years).
 
And added: To describe the following endpoints and compare them between arms: DRFS, OS
 
 
• Section 6.8 Surveillance (this was previously submitted as a protocol clarification letter on April 28,2021)
 
 
CURRENTLY STATES: Participants will be monitored by their treating physicians for the development of either local (chest wall, axillary, or supraclavicular nodes) or distant recurrent disease at least once every 3 months for the first two years, then at least every 6 months during year 3.
 
UPDATED TO: Participants will be monitored by their treating physicians for the development of either local (chest wall, axillary, or supraclavicular nodes) or distant recurrent disease, and survival, at least once every 3 months for the first two years, then at least every 6 months during year 3.

--	--	--

TABLE OF CONTENTS		Page
Table of Contents		8
Study Synopsis		10
1.0	Background and Justification	
1.1	Triple negative breast cancer and residual disease	12
1.2	Immunotherapy as a treatment option for TNBC	12
1.3	The immune milieu in TNBC	13
1.4	Evaluating anti-tumor immunity in the absence of measurable disease	13
1.5	Nivolumab Activity and Pharmacokinetic Profile	14
1.6	Patient reported outcomes (PRO)	18
1.7	Rationale for the Current Study	19
2.0	Study Objectives	
2.1	Primary Objectives	20
2.2	Secondary Objectives	20
3.0	Study design	21
4.0	Subject Population	
4.1	Subject Population, Number of Subjects, and Feasibility	22
4.2	Inclusion Criteria	22

## STUDY SYNOPSIS

Title	OXEL: A pilot study of immune checkpoint or capecitabine or combination therapy as adjuvant therapy for triple negative breast cancer with residual disease following neoadjuvant chemotherapy
Short Title	OXEL study
Protocol Number	2017-1535 (Georgetown University Parent IRB); BMS CA209-8CL
Clinicaltrials.gov number:	NCT03487666
Phase	Phase 2
Investigational Agents	Nivolumab, a PD-1 monoclonal antibody (BMS)
Indication	Advanced triple negative breast cancers
Study Overview	This is a pilot phase II trial for patients with triple negative breast cancer.
Study Duration	36 months
Study Center(s)	
 
➤ Georgetown University, Lombardi Comprehensive Cancer Center Washington, DC
 
➤ MedStar Washington Hospital Center, Washington DC
 
➤ Hackensack University Medical Center, Hackensack, NJ
 
➤ One additional participating center to be determined
 

Objectives	
Primary objective: To assess the immunologic effects of capecitabine, nivolumab or the combo, post neoadjuvant and post-surgery, in the adjuvant setting, in patients with high risk TNBC as defined by presence of residual disease (breast and or LNs) at surgery, in terms of the change of PIS.
 
Secondary objectives:
 
 
1) To determine the incidence of toxicity graded using the National Cancer Institute CTCAE v. 4.0 until 30 days after last dose of treatment on trial.
 
2) To determine association between changes in PIS from baseline to week 6 and week 12 and clinical outcome variables (DRFS and OS at 2-years).
 
3) To describe the following endpoints and compare them between arms: DRFS, OS
 
4) Translational endpoints:             
 
a) circulating tumor DNA (ct-DNA) during treatment
 
 
 
 
Exploratory objectives:
 
 
a) To describe the immune contexture in residual tumors of patients with high risk TNBC after receiving neoadjuvant chemotherapy
 
b) Tissue banking for future studies (NGS of initial biopsy and surgical specimen), plasma, PBMCs
 

Number of Subjects	The anticipated number of patients will be 45.

Diagnosis and Main Inclusion and Exclusion Criteria	
Key Inclusion Criteria: Biopsy proven TNBC (ER and PR defined as <math>\leq 5\%</math> cells stain positive), HER2 negativity defined as (IHC0, 1+ without in situ hybridization (ISH) HER2/neu chromosome 17 ratio OR IHC 2+ and ISH HER2/neu chromosome 17 ratio non-amplified with ratio <math>< 2.0</math> and if reported average HER2 copy number <math>< 6</math> signals/cells); residual disease of <math>\geq 1.0</math> cm of the primary tumor and/or node positive disease measuring <math>\geq 0.5</math>cm; receipt of neoadjuvant taxane +/- anthracycline; platinum use allowed; must have completed definitive resection of primary tumor; signed ICF; age <math>\geq 18</math>.
 
Key Exclusion Criteria: Stage IV disease; previous exposure to capecitabine, fluorouracil or immunotherapy with anti-PD1, anti PDL1 or anti-CTLA4; active autoimmune disease requiring systemic treatment in the past 2 years; tuberculosis, hepatitis B or C, HIV or other active infection; chronic use of systemic steroids or pregnancy.

Study Design	
Pilot phase II open-label three arm randomized trial of nivolumab, capecitabine or combination as adjuvant therapy for 45 patients with residual TNBC after adequate neoadjuvant chemotherapy followed by definitive surgery. Patients are randomly assigned to 1 of 3 treatment arms: ARM A – Nivolumab 360 mg iv q3weeks for x 6 cycles; ARM B - Capecitabine 1250mg/m^2 bid D1-D14 q3 weeks x 6 cycles; ARM C - Nivolumab 360mg iv q3weeks + Capecitabine 1250mg/m^2 bid D1-D14 q3 weeks x 6 cycles. We will enroll 15 patients per arm (45 totally for 3 arms).

Duration of therapy	
All drugs will be administered for 18 weeks, or until disease progression or unacceptable toxicity is observed.

Sample size considerations	
The primary objective of the study is to assess the change in PIS, the Peripheral ImmunoScore, at 6 weeks (=2 cycles) from baseline, in each arm. The sample size of 15 per arm (45 totally for 3 arms) is mainly based on the feasibility of patient accrual. A sample size of 15 per arm will have about 85% power to detect an effect size of 1 (the difference of the change in PIS from baseline to week 6 between two arms divided by the standard deviation) at 5% significance level.

## 1.0 BACKGROUND AND JUSTIFICATION

[figure not shown]
### 1.1. Triple negative breast cancer and residual disease

Breast cancer (BC) is the most common cancer in women in the United States, with an estimated 252,710 new cases of invasive BC anticipated in 2017. Overall, triple negative breast cancer (TNBC) accounts for 10-15% of invasive BC cases and it is associated with a worse prognosis and limited treatment options compared to the other subtypes. Patients with TNBC and residual disease at the time of surgery after completing neoadjuvant chemotherapy constitute a group of patients at a high risk of recurrence. Long-term follow-up of neoadjuvant studies consistently demonstrates worse clinical outcomes in patients with TNBC who did not achieve pathologic complete response (pCR), with only 35-40% remaining free of recurrence at 2 years. Until recently, the standard of care for patients with early stage TNBC who do not achieve pCR was observation or participation in a clinical trial. More recently, adjuvant capecitabine became an option after the CREATE-X study revealed that the addition of adjuvant capecitabine prolonged disease-free survival (DFS) and overall survival (OS) among patients with HER2-negative BC who had residual invasive disease on pathological testing. This benefit was more striking in patients with TNBC (DFS 69.8% in the capecitabine group vs 56.1% in the control group, HR 0.58; 95% CI, 0.39 to 0.87; and OS 78.8% vs 70.3%, HR 0.52; 95% CI, 0.30 to 0.90).

### 1.2. Immunotherapy as a treatment option for TNBC

Immunotherapy has shifted the treatment paradigm for many malignancies, but not all cancer types have enjoyed a clinically meaningful response from checkpoint blockade. In BC, most work to date with immunotherapy has focused on TNBC given the greater frequency of tumor infiltrating lymphocytes (TILs). The overall response rate (ORR) in heavily pretreated patients with TNBC who received pembrolizumab single agent was 18.5%. Other trials in TNBC either

in the metastatic or neoadjuvant setting, have shown that the combination of immune checkpoint inhibitors plus chemotherapy may be a more promising approach. In the phase I clinical trial of atezolizumab and nabpaclitaxel, in patients with metastatic disease those treated in first line derived the greatest benefit, when compared to patients treated in second or third line (ORR 67% vs 25-29% in 1st line versus 2nd/3rd line respectively). These findings confirm the overall impression that when chemoimmunotherapy is used earlier in TNBC, the outcome is better. They also support the notion that, in TNBC, the addition of chemotherapy to a checkpoint inhibitor is a promising strategy, contrary to what is observed in less chemosensitive diseases such as melanoma.

**Figure 1.** Genome-wide shRNA library screen in EO771 TNBC tumors growing in WT or SCID C57Bl/6 mice reveals genes whose knockdown either reduces (left, upper) or increases (right, upper) the representation of the targeted tumor cells in 1

### 1.3. The immune milieu in TNBC

It is unlikely that immunotherapy alone or in combination with chemotherapy will be effective in all patients with residual TNBC after neoadjuvant chemotherapy. Thus, we need to characterize the immune contexture of the residual tumors in order to select patients who will benefit additional therapy including immunotherapy. Many tools are available to describe the immune contexture in the tumor microenvironment, using powerful technologies such as multiplex immunohistochemistry (IHC), genome-wide association studies (GWAS) and mass cytometry. Recently we employed a genome-wide shRNA screen to identify 709 genes that selectively regulated adaptive anti-tumor immunity in a syngeneic, functionally TNBC model and focused on five genes (CD47, TGFβ1, Sgpl1, Tex9 and Pex14) with the greatest impact as biomarkers of resistance (Fig. 1). We have used this same approach to identify genes that regulate resistance to PD-1 antibody directed immune attack in the same TNBC model (not shown). While work done using The Cancer Genome Atlas (TCGA) data to characterize immune cell infiltrates in TNBC is valuable and foundational it may not accurately reflect the immune milieu of tumors resistant to chemotherapy. This is the rationale to the evaluation of the immune contexture in tumors that are resistant to neoadjuvant chemotherapy, in order to guide future adjuvant therapy approaches for these patients at a high risk of recurrence.

### 1.4. Evaluating anti-tumor immunity in the absence of measurable disease

A significant challenge in evaluating the effects of experimental adjuvant therapies is the lack of measurable disease to assess therapeutic effects. In this setting, when tumor is not detectable such as in patients with early BC who have undergone surgical resection of their tumor, the identification of biomarkers in the peripheral blood – the most readily available tissue for sampling – to assess effects of the intervention is intuitively attractive. Immune cell subsets within peripheral blood mononuclear cells (PBMC) have been analyzed to determine if a peripheral immunoscore could have any prognostic significance for patients undergoing immunotherapy. Although to date there is no validated FDA-approved circulatory immunological biomarker for patients with breast cancer, the refined peripheral immunoscore (PIS) defined by

Criterion 1: Classic cell types		Criterion 2: Phenotypes of refined cell subsets reflecting immune function		
Description	Expected effect on PFS	Description	Expected effect on PFS	Reference
% CD4	Positive	% Central memory CD4 hi	Positive	(9)
		% CD4 expressing ≥2 suppressive markers 	Negative	(20, 21)
% CD8	Positive	% Central memory CD8 hi	Positive	(9)
		% CD8 expressing ≥2 suppressive markers 	Negative	(20, 21)
% Treg 	Negative	% Treg CD45 lo	Negative	(22, 23)
% MDSC 	Negative	% MDSC Lin  	Negative	(24, 25)
% NK 	Positive	% NK CD56 hi CD16 +	Negative	(26, 27)
Ratio CD4:Treg	Positive	Ratio central memory  CD4:Treg CD45 lo	Positive	
Ratio CD8:Treg	Positive	Ratio central memory  CD8:Treg CD45 lo	Positive	
Ratio CD4:MDSC	Positive	Ratio central memory  CD4:MDSC Lin 	Positive	
Ratio CD8:MDSC	Positive	Ratio central memory  CD8:MDSC Lin 	Positive	
		Ratio central memory  CD4:NK CD56 hi CD16 +	Positive	
		Ratio central memory  CD8:NK CD56 hi CD16 +	Positive	

NOTE: Frequencies of PBMC subsets represented as a percentage of total PBMCs.  CD45RA+CCR7+;  CTLA-4, PD-1, Tim-3, 2B4;  CD4+CD25+FoxP3+CD127;  CD3CD16CD19CD20^-CD56CD33HLA-DR^-HLA-DR^-HLA-DR^-;  CD14+CD15+;  CD3CD56.

Table 1. Refined peripheral immunoscore

Farsaci et al (Table 1) was validated in a group of patients with metastatic BC receiving docetaxel and immunotherapy, and shown to be predictive of progression free survival (PFS). When compared to predefined analyses of "classic" immune cell types (CD4, CD8, natural killer cells, regulatory T cells, myeloid-derived suppressor cells, and ratios) that revealed no differences in PFS for either arm

(docetaxel alone or docetaxel with vaccine), predefined analyses of refined immune cell subsets for which a biologic function had been previously reported revealed statistically significant improved PFS ( $P < 0.001$ ) for those receiving docetaxel plus immunotherapy (Fig 2). Based on these results, we selected for our study the PIS as a surrogate of clinical benefit and a new strategy to identify patients with BC who may benefit from immunotherapy to eliminate residual micrometastasis.

[figure not shown]
[figure not shown]

Figure 2.a Docetaxel alone

Figure 2.b Docetaxel and vaccine

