### **1.5.2. Nonclinical Studies**

Nivolumab has been shown to bind specifically to the human PD-1 receptor and not to related members of the CD28 family. Nivolumab inhibits the interaction of PD-1 with its ligands, PD-L1 and PD-L2, resulting in enhanced T-cell proliferation and interferon-gamma (IFN- $\gamma$ ) release in vitro. Nivolumab binds with high affinity to activated human T-cells expressing cell surface PD-1 and to cynomolgus monkey PD-1.2 In a mixed lymphocyte reaction (MLR), nivolumab promoted a reproducible concentration-dependent enhancement of IFN- $\gamma$  release. In intravenous (IV) repeat-dose toxicology studies in cynomolgus monkeys, nivolumab was well tolerated at doses up to 50 mg/kg, administered weekly for 5 weeks, and at doses up to 50 mg/kg, administered twice weekly for 27 doses. While nivolumab alone was well tolerated in cynomolgus monkeys, combination studies have highlighted the potential for enhanced toxicity when combined with other immunostimulatory agents.

In addition, an enhanced pre- and postnatal development (ePPND) study in pregnant cynomolgus monkeys with nivolumab was conducted. Administration of nivolumab at up to 50 mg/kg 2QW was well tolerated by pregnant monkeys; however, nivolumab was determined to be a selective developmental toxicant when administered from the period of organogenesis to parturition at  $\geq 10$  mg/kg (area under the concentration-time curve [AUC] from time zero to 168 hours [AUC(0-168 h)] 117,000  $\mu\text{g}\cdot\text{h}/\text{mL}$ ). Specifically, increased developmental mortality (including late gestational fetal losses and extreme prematurity with associated neonatal mortality) was noted in the absence of overt maternal toxicity. There were no nivolumab-related changes in surviving infants tested throughout the 6-month postnatal period. Although the cause of these pregnancy failures was undetermined, nivolumab-related effects on pregnancy maintenance are consistent with the established role of PD-L1 in maintaining fetomaternal tolerance in mice.

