### 1.5.4. Clinical Pharmacokinetics

The PK of nivolumab was studied in subjects with cancer over a dose range of 0.1 to 20 mg/kg administered as a single dose or as multiple doses of nivolumab every 2 or 3 weeks. Nivolumab clearance (CL) decreases over time, with a mean maximal reduction (% coefficient of variation [CV%]) from baseline values of approximately 24.5% (47.6%) resulting in a geometric mean steady state clearance (CLss) (CV%) of 8.2 mL/h (53.9%); the decrease in CLss is not considered clinically relevant. The geometric mean volume of distribution at steady state (Vss) was 6.8 L (27.3%), and geometric mean elimination half-life (t1/2) was 25 days (77.5%). Steady-state concentrations of nivolumab were reached by 12 weeks when administered at 3 mg/kg Q2W, and systemic accumulation was approximately 3.7-fold. The exposure to nivolumab increased dose proportionally over the dose range of 0.1 to 10 mg/kg administered every 2 weeks. Additionally, nivolumab has a low potential for drug-drug interactions. The clearance of nivolumab increased with increasing body weight. The PPK analysis suggested that the following factors had no clinically important effect on the CL of nivolumab: age (29 to 87 years), gender, race, baseline LDH, PD-L1 status, solid tumor type, baseline tumor size, and hepatic impairment. Although ECOG status, baseline glomerular filtration rate (GFR), albumin, and body weight had an effect on nivolumab CL, the effect was not clinically meaningful. PPK analysis suggest that nivolumab CL in subjects with cHL was approximately 32% lower relative to subjects with NSCLC; however, the lower CL in cHL subjects was not considered to be clinically relevant as nivolumab exposure was not a significant predictor for safety risks for these patients. When nivolumab is administered in combination with ipilimumab, the CL of nivolumab was increased by 29%, whereas there was no effect on the clearance of ipilimumab. PPK and exposure response analyses have been performed to support use of nivolumab 240 mg Q2W, 360 mg Q3W, and 480 mg Q4W dosing regimens in subjects with cancer in addition to the 3 mg/kg Q2W regimen. A flat dose of nivolumab 240 mg Q2W was selected since it is identical to a dose of 3 mg/kg for subjects weighing 80 kg, the observed median body weight in nivolumab treated cancer patients, while the nivolumab 360 mg Q3W and 480 mg Q4W regimens allow flexibility of dosing with less frequent visits and in combination with other agents using alternative dosing schedules to Q2W. Using a PPK model, the overall distributions of nivolumab exposures (Cavgss, Cminss, Cmaxss, and Cmin1) are comparable after treatment with either nivolumab 3 mg/kg or 240 mg Q2W. Following nivolumab 360 mg Q3W and 480 mg Q4W, Cavgss are expected to be similar to those following nivolumab 3 mg/kg or 240 mg Q2W, while Cminss are predicted to be 6% and ~16% lower, respectively, and are not considered to be clinically relevant. Following nivolumab 360 mg Q3W and 480 mg Q4W, Cmaxss are predicted to be approximately ~23% and ~43% greater, respectively, relative to that following nivolumab 3 mg/kg Q2W dosing. However, the range of nivolumab exposures (median and 90% prediction intervals) following administration of 240 mg flat Q2W, 360 mg Q3W, and 480 mg Q4W regimens across the 35 to 160 kg weight range are predicted to be maintained well below the corresponding exposures observed with the well tolerated 10 mg/kg nivolumab Q2W dosing regimen. In this study we will use the flat dose of 360mg Q3W. Although this is a less frequent dosing regimen, it will

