## **8.5 Analysis Plan**

### **8.5.1. Analysis for the Primary Endpoint**

For the primary endpoint, the observed change of PIS from baseline to week 6 in each arm will be presented with its 95% confidence interval. The difference of the change of PIS between treatment arms will be compared using two-sample t-test.

For a patient to be evaluable for immunomodulation, measured by the peripheral immunoscore, by nivolumab, capecitabine or the combo, the patient must complete the first 2 cycles. Any patient who is taken off study prior to completion of 2 cycles must be replaced.

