## **9.0 CORRELATIVE RESEARCH**

### **9.1 Peripheral Immunoscore**

We selected the refined PIS as a surrogate of clinical benefit and a new strategy to identify patients with TNBC and high-risk disease who may benefit from immunotherapy to eliminate residual micrometastasis. The peripheral immunoscore was calculated based on a predefined analyses of refined immune cell subsets for which a biologic function had been previously reported revealed statistically significant improved PFS ( $P < 0.001$ ) in patients with metastatic breast cancer receiving docetaxel plus immunotherapy compared to docetaxel alone (Fig 2). To calculate the PIS, flow cytometry was performed on PBMC harvested at different time points. A multiparametric flow cytometry platform was applied to measure the frequency of PBMC. Patients' PBMCs by density gradient separation, and then 1 mL of PBMCs was cryopreserved in liquid nitrogen at a concentration of 107 cells/mL per vial. On the day of staining, one vial of cryopreserved PBMCs per patient was defrosted, cells were counted, and then stained with the appropriate monoclonal antibodies. Table 1 shows the classic immune cell types as well as those refined subsets with a phenotype reflecting immune function. Viability of all samples following thawing after cryopreservation was 80% to 95%. The frequency of individual subsets was calculated as a percentage of total PBMCs to help reduce the bias that could occur in the smaller subpopulations with fluctuations in parental leukocyte populations. The PIS defined by Farsaci et al was selected based on being the closest to the particular scenario proposed on the OXEL study. This has been validated in a group of patients with metastatic BC receiving docetaxel and immunotherapy, and shown to be predictive of PFS. While this (and other) immune biomarkers in the blood available today have not been validated in all clinical scenarios – including early BC – available data suggests that this immunoscore constitutes a promising surrogate marker of clinical outcome in this group of patients. The PIS will be performed 40) at [name] lab at NIH, which developed this particular immunoscore.

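### PIS counts PD-1 as a suppressive marker and nivolumab binds PD-1, so the primary comparison needs a supportive PIS without PD-1 in case bound drug masks the stain

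*Combined protocol and SAP*

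**What the plan says.** Section 9.1 adopts the refined version of the score ("We selected the refined PIS"). Table 1 in section 1.4 lists its components under Criterion 2. Two of them are "CD4 expressing ≥2 suppressive markers" and "CD8 expressing ≥2 suppressive markers", each with a negative expected effect on PFS. The table note gives the marker set as "CTLA-4, PD-1, Tim-3, 2B4".

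On the drug, section 1.5.2 states: "Nivolumab has been shown to bind specifically to the human PD-1 receptor". It adds: "Nivolumab binds with high affinity to activated human T-cells expressing cell surface PD-1". Section 1.5.4 gives an elimination half-life of 25 days.

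The primary endpoint (8.4.1) is the change in PIS from baseline to week 6. Sections 2.1 and 8.1 expect this change to be larger in arms A and C than in arm B. Section 8.5.1 has one comparison of one score: "The difference of the change of PIS between treatment arms will be compared using two-sample t-test". Section 9.1 does not name the PD-1 staining antibody, and sections 6.5, 6.6 and 9.3 refer to a Correlative Laboratory Manual for further detail.

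**The concern.** The treatment and the assay share a target. Nivolumab sits on the molecule that two score components are meant to detect, and it does so after baseline and in two arms only. If bound drug hides PD-1 from the staining antibody, some cells that truly carry two suppressive markers will be counted as carrying one. The suppressive fractions would fall and, because those rows are labelled Negative, the score would be expected to rise.

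That would bias A v B and C v B towards the stated hypothesis; A v C would share the artefact. The PIS change is the only primary endpoint, and the protocol treats it as a surrogate of clinical benefit. The primary analysis as written has no version of the score that would show whether a difference rests on the PD-1 stain.

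**Working it through.** **The plan's own figure.** Section 8.2 claims about 85% power for a 1 SD difference with 15 per arm at the 5% level. The noncentrality is 1/√(1/15 + 1/15) = 2.74 on 28 degrees of freedom. The t-test power is 84.8% one-sided and 75.3% two-sided, so the claim reproduces one-sided only. It is not disputed here; the same test is used below.

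**Is drug present at the sample?** Inputs are the 25-day half-life (1.5.4), dosing every 3 weeks (5.2) and sampling at week 6 (6.1, 6.6). By simple exponential decay, the fraction of a dose left after 21 days is 2^(−21/25) = 0.56, and after 42 days 2^(−42/25) = 0.31. The first two doses together leave 0.56 + 0.31 = 0.87 of one dose at day 42. Drug is probably present. This is not a receptor-occupancy figure, and the documents give none.

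**How much of the score is exposed?** Criterion 2 has 7 subset percentages and 6 ratios, 13 in all. Only the two suppressive-marker rows use the list: 2/13 = 15%. The footnote tags in the table as supplied are scrambled, but no other row calls for a marker list.

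**How far could those two fractions fall?** A cell leaves the subset only if PD-1 was one of exactly two positive markers. Assume total loss of the PD-1 signal and four independent markers, each positive with probability p:

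- p = 0.1: P(≥2 of 4) = 0.052, P(≥2 of 3) = 0.028, a relative fall of 46%.
- p = 0.3: 0.348 and 0.216, a fall of 38%.

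If the markers are positively correlated (shared normal latent factor, correlation 0.5 to 0.7), the fall is roughly 18 to 32%. Partial masking would reduce it further.

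**What could that do to the test?** The documents give neither the rule that combines components into PIS nor the SD of the change. Purely for illustration, take an equally weighted sum of 13 standardised components with common correlation ρ, and shift the two exposed components by s SD. Then d = 2s/√(13 + 156ρ), where the denominator is 3.61 for ρ = 0 and 7.73 for ρ = 0.3. The table gives rejection rates with no true effect, two-sided 5%:

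| s | ρ | d | 15 v 15 | A+C (30) v B (15) |
|---|---|---|---|---|
| 0.1 | 0.3 | 0.03 | 5.1% | 5.1% |
| 0.1 | 0 | 0.06 | 5.2% | 5.3% |
| 0.25 | 0.3 | 0.06 | 5.3% | 5.5% |
| 0.25 | 0 | 0.14 | 6.6% | 7.1% |
| 0.5 | 0.3 | 0.13 | 6.4% | 6.9% |
| 0.5 | 0 | 0.28 | 11.4% | 13.8% |
| 1 | 0.3 | 0.26 | 10.5% | 12.6% |
| 1 | 0 | 0.55 | 31.1% | 40.3% |

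Nothing in the documents links the percentage fall in the fractions to a value of s, so no row can be called the expected one.

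**The case against.** The deciding fact is missing. Masking needs a staining antibody that competes with bound nivolumab, and the documents are silent on this. Section 9.1 assigns the assay to the laboratory that developed the score, and the laboratory manual, which is not part of these documents, may name a non-competing reagent. If it does, the problem disappears. This stands, and it is why the point is conditional.

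The numbers are also soft. The scoring rule is not given, the direction is inferred from the Negative label, and the largest rates need a 1 SD shift with uncorrelated components. This stands too: the lower half of the table is close to nominal.

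A reader might infer that an artefact could never be told apart from real activation. The documents do not support that. Section 8.4.3 lists exploratory readouts, including intracellular cytokine staining and CD8+ T-cell clonal expansion, that do not rest on surface PD-1 staining. However, section 8.5 sets out no analysis that ties them to the PIS result.

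A reader might also infer that the PD-1-free score should become primary, or that both versions must agree before any claim. That goes too far. The protocol relies on the published score for its link to PFS and gives no PFS data for a variant. An agreement rule also cannot add power to a test that has about 75% two-sided.

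**Conclusion.** The structural risk is real. PD-1 enters two negatively labelled components, the drug binds PD-1, exposure differs by arm, the possible bias runs in the hypothesised direction, and section 8.5.1 contains no check. Bias itself is not shown. It depends on three things the documents do not settle: competition between the staining antibody and bound drug, occupancy of PD-1 at week 6, and a scoring rule in which fewer suppressive-marker cells raise PIS.

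The size is unknown. Under the illustrative score, the two-sided false-positive rate at 15 v 15 runs from about 5% to 31%, staying at 5 to 7% for shifts of 0.1 to 0.25 SD. With 11 of 13 components untouched, a small effect is quite possible. A reader might take the documents to show that PIS will be inflated in arms A and C; they show only that it could be. A low-cost supportive analysis is proportionate to that.

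**What to change.** In section 8.5.1, before any between-arm PIS results are seen:

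- Prespecify a supportive sensitivity analysis that recomputes PIS from the same flow data with PD-1 left out of the suppressive-marker count (at least 2 of CTLA-4, Tim-3 and 2B4).
- Repeat the A v B and C v B comparisons of week-6 change with this version and report them beside the primary result.
- State that the claim of immune activation by nivolumab will be limited if the difference depends on the PD-1 component. Such dependence would not prove an artefact, because a true fall in PD-1 expression would look the same.
- Confirm with the assay laboratory, and record, whether its PD-1 antibody is affected by bound nivolumab.

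Keep the published PIS as the primary endpoint. The cost is a few lines of text, one query to the laboratory and one recomputation, with no new samples or visits. The small downside is an extra analysis on a score variant for which the documents give no PFS data.
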